## 2. Background Information

Emergency contraception (EC) is used to prevent unwanted pregnancy after unprotected sexual intercourse (UPSI) or after a recognised contraceptive failure such as condom accidents or missing doses of hormonal contraception. Availability of effective EC methods is very important for reducing the occurrence of unwanted pregnancies in these circumstances.

Oral hormonal EC is the most widely adopted EC method in both Hong Kong and most other countries. The EC method currently available for oral use consists of a single dose of 1.5 mg levonorgestrel (LNG) to be taken within 72 hours of UPSI, or 30 mg ulipristal acetate (UPA) to be taken within 120 hours of UPSI (Glasier et al, 2014; Faculty of Sexual and Reproductive Health, 2017).

Studies have shown that LNG is effective as an EC only when given before, but not after, ovulation (Novikova et al, 2007; Noe et al, 2010). This may be explained by its mechanism of action. LNG prevents pregnancy by blocking or postponing the luteinizing hormone (LH) surge, hence disrupting the ovulatory process; this effect is limited to its administration before the onset of the LH surge, but not when it is taken after the LH surge has commenced, a time when intercourse is most likely to result in pregnancy. The more advanced in the follicular phase that LNG is taken, the lower will be its ability to block ovulation and thus prevent fertilization after UPSI (Croxatto et al, 2004). Once the ovulatory process has been triggered by the LH surge, LNG cannot prevent the follicle from rupturing and releasing the oocyte. It was also shown that LNG has no effect on sperm function, fertilization and implantation (Cameron et al, 2017).

UPA, another selective progesterone receptor modulator, has more recently been introduced as an oral EC. Two randomized controlled trials showed that UPA was as effective as LNG for EC within 72 hours of UPSI (Creinin et al, 2006; Glasier et al, 2010). When the results of the two RCTs were combined in a meta-analysis, UPA has significantly lower failure rate compared to LNG [1.36% (22/1617) vs 2.15% (35/1625),  $p=0.046$ ] (Glasier et al, 2010). The effectiveness of UPA as EC is maintained up to 120 hours after UPSI, which is currently the licensed indication of UPA. In contrast to LNG which has a limited administration period preceding the onset of the LH surge for it to be effective, it was demonstrated that a single dose of 30 mg UPA administered up till the time immediately before the LH peak could still significantly interfere with follicular rupture (Brache et al, 2010). It was initially postulated in some studies that UPA might also have some concurrent inhibitory effect on embryo implantation based on changes in some molecular and histological parameters induced by UPA, but this was not supported by subsequent in-vitro co-culture experiments. One study in Hong Kong also did not support a significant clinical effect of UPA as EC when administered post-ovulation (Li et al, 2016). Therefore, the journey in search of further improvement in the efficacy of oral EC methods, particularly one with effective post-ovulatory action, still continues.

Prostaglandins are “local hormones” that take part in a number of reproductive processes including ovulation (Duffy, 2015), fertilisation (Sugimoto et al, 2015), tubal function (Wanggren et al, 2006; Wanggren et al, 2008) and embryo implantation (Salleh, 2014). Hence, it is postulated that an inhibitor of the cyclo-oxygenase (COX) enzyme, the key enzyme involved in prostaglandin production, may potentially confer a “contraceptive”

effect and may act synergistically with LNG for EC, particularly to target at the post-ovulatory events in addition.

Existing clinical trials which explored the effect of several COX-2 inhibitors on ovulatory function were reviewed in a recent publication (Weiss and Gandhi, 2016); this included six clinical trials exploring the effect of rofecoxib, meloxicam and celecoxib on human ovulatory function. It was suggested that administration of these COX-2 inhibitors in the follicular phase could disrupt or delay follicle rupture, but in most of these studies the drug was administered consecutively for at least 5 days, which would be inconvenient in the context of emergency contraception and compliance may be an issue. Only one study explored the use of a single dose of meloxicam concurrently with LNG 1.5 mg; a trend of increased incidence of unruptured follicles was reported in the LNG plus meloxicam group compared to the LNG plus placebo group, and yet statistical significance was not reached, probably due to the small sample size (n=41). There were little data on the clinical effect of COX inhibitors on post-ovulatory events such as embryo implantation.

Based on the above information, we hypothesize that inhibition of prostaglandin synthesis by a COX inhibitor may confer additional contraceptive action when administered in adjunct to the current LNG regimen, as this may result in disruption of both ovulatory and post-ovulatory events involved in the establishment of conception. Blocking prostaglandin synthesis may retard tubal activities and hence slow down embryo transport, leading to delayed arrival of the embryo to the uterine cavity beyond the implantation window. Furthermore, any negative effect of reduced prostaglandin synthesis on endometrial receptivity may further potentiate its contraceptive action. Hence, it is hoped that COX inhibitor and LNG may act synergistically to achieve an enhanced efficacy for EC.

We choose to investigate the effect of piroxicam, one of the longest-acting COX inhibitor (with half-life over 50 hours) that is commercially available, at a single oral dose of 40 mg. An oral dose of piroxicam up to 40 mg is used pharmacologically for pain relief. Although small clinical studies in women undergoing assisted reproduction treatment showed that a low dosage (10 mg) of piroxicam did not interfere with, or might even enhance, implantation rate (Moon et al, 2004; Firouzabadi et al, 2007; Dal Prato and Borini, 2009; Kumbasar et al, 2017), it is probable that a higher dose may prevent implantation.

### 3. Objectives:

Aim: To compare the percentage of pregnancies prevented by LNG co-administered with piroxicam or placebo for oral emergency contraception by a randomised controlled trial.

Hypothesis to be tested: LNG plus piroxicam has higher percentage of pregnancies prevented compared with LNG plus placebo for oral emergency contraception.

### 4. Study design:

This will be a randomised placebo-controlled double-blind clinical trial. A dedicated research nurse will help coordinate subject recruitment, study administration and follow-up of subjects. Subjects who give written consent to participate in this study shall be randomised to either the piroxicam arm (Treatment group) or placebo arm (Placebo group) in 1:1 ratio according to a computer-generated randomisation list in blocks of 10 in sealed envelopes which are prepared by an independent person. The medication will be prepacked by an authorised third party not directly involved in this study. The subjects, clinicians and research staff will be blinded to the group assignment. The codes for the treatment groups will only be revealed to the investigators after completion of the whole study and statistical analyses. It is anticipated that subject recruitment shall take 20 months; follow-up of the subjects will be completed in 2 months further, and a summary of preliminary results will be available by 24 months.

### 5. Subject selection and exclusion

#### 5.1 Inclusion criteria

Women attending the Family Planning Association of Hong Kong for oral EC will be recruited if they fulfil the following criteria:

- (a) healthy women aged 18 years or above;
- (b) requesting emergency contraception within 72 h of a single act of unprotected intercourse in the current menstrual cycle;
- (c) having menstrual cycles between 24 and 42 days
- (d) willing to abstain from further acts of unprotected intercourse and;
- (e) available for follow-up over the next 6 weeks.

#### 5.2 Exclusion criteria

- (a) post-abortion or postpartum and period have not yet returned,
- (b) being on the following drugs currently: anticoagulants, cyclosporine, tacrolimus, corticosteroids, lithium, serotonin reuptake inhibitors (SSRIs), quinolones
- (c) having unprotected intercourse in this cycle more than 72 hours or more than once before attending the clinic,
- (d) being found pregnant at the time of presentation,
- (e) breastfeeding,
- (f) having been sterilized (or partner having been sterilized) or having intrauterine contraceptive device in-situ,
- (g) uncertain about the date of the last menstrual period,
- (h) having used hormonal contraceptive (including EC pill) in the current or past one cycle, or NSAID in the recent one week,

- (i) having history of asthma, urticaria or other allergic reactions to piroxicam, aspirin or other NSAIDs,
- (j) having history of ischaemic heart disease, heart failure, hypertension or cerebrovascular disease
- (k) having history of peptic ulcer disease and/or gastrointestinal bleeding

The proposed start date of this study is 1 August 2018, and it is anticipated that study recruitment will last for two years.

## 6. Treatment of subjects

### 6.1 Baseline assessment:

- The subject will be assessed and counselled for the use of EC by the clinic nurse or doctor as routine. Suitable subjects will be enrolled for the study after informed consent.
- A menstrual history will be taken.
- Pregnancy test will be done; only those tested negative will be recruited into study.
- Blood (5 ml into clotted bottle) will be collected for hormonal assay (LH, oestradiol, progesterone). The serum hormonal levels will be used to estimate the cycle day at the time of presentation in relation to the day of ovulation based on the method described by Novikova et al (2007).

### 6.2 Treatment:

After counselling and obtaining informed consent, eligible subjects will be randomised to receive one of the two treatment regimens, i.e. Treatment group: a single dose of LNG 1.5 mg and piroxicam 40 mg, or Placebo group : a single dose of LNG 1.5mg and placebo under direct supervision. The subject and the research staff responsible for subject follow-up will be blinded to the treatment arm.

The subjects will be advised not to have further acts of coitus before menstruation returns. They will be given a diary chart to record vaginal spotting and bleeding, possible side effects and further acts of intercourse, if any, and the contraceptive method used.

### 6.3 Follow-up:

A follow-up appointment will be arranged about 1-2 weeks after the next expected menstruation. Information collected at the follow-up visit will include side effects and vaginal bleeding/spotting marked by the subject on her diary card; time of onset, duration and amount of menstrual bleeding and any further acts of intercourse and the type of contraception used (refer to Appendix 1).

If normal menstrual bleeding has not occurred by that time, a pregnancy test will be carried out, and a positive result denotes treatment failure and the woman will be counselled accordingly. If the woman opts for continuing with pregnancy, she will be referred for antenatal care. An additional research follow-up will be arranged post-delivery to record any antenatal, postnatal and neonatal complications. If the woman opts for terminating the pregnancy, she will be referred to the appropriate services.

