## 7. Study outcomes

### Primary outcome measure:

- Fraction of pregnancies prevented (%)  
[(expected pregnancies – observed pregnancies] / expected pregnancies]  
The number of expected pregnancies will be determined by the Trussell's model (Trussell J et al, Contraception 2003; 67:259-265)

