### Secondary outcome measures:

- Pregnancy rate (%)
- Change in length (shortening / lengthening) of current cycle (days)
- Adverse effects

The data collection sheet is included in Appendix 1. All the clinical data are part of the usual consultations for EC provision.

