## 9.2 Sample size estimation:

In a previous study on using LNG for EC within 72 hours of UPSI (Glasier et al, 2010), the fraction of prevented pregnancies was 51.9% based on the Trussell's model. With the assumption that the fraction of prevented pregnancies in the placebo group is around 52%, and the fraction of prevented pregnancies in the treatment group should be at least 10% higher than that in the placebo group for it to be clinically meaningful, a minimum of 384 subjects in each group will be required to demonstrate superiority of the proposed treatment with a power of 80% and type I error of 0.05. Assuming that around 10% of the subjects may default follow-up, we plan to recruit a total of 860 subjects.

No interim analysis is planned as it is anticipated that co-administration of oral piroxicam with LNG will not adversely reduce its EC efficacy.

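### Section 6.3 does not test women whose bleed is accepted as normal menses, so a missed pregnancy counts as prevented and raises that arm's prevented fraction

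*Combined protocol and SAP*

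**What the plan says.** Section 6.3 plans one outcome contact: "A follow-up appointment will be arranged about 1-2 weeks after the next expected menstruation". Diary entries on bleeding and spotting are reviewed there, together with "time of onset, duration and amount of menstrual bleeding". The test itself is conditional: "If normal menstrual bleeding has not occurred by that time, a pregnancy test will be carried out", and "a positive result denotes treatment failure". The section does not say what makes a bleed normal or who decides, and it names no pattern in the recorded bleeding that would trigger a test.

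The only other pregnancy test is for eligibility, in section 6.1: "Pregnancy test will be done; only those tested negative will be recruited into study". The extra post-delivery contact in 6.3 concerns only pregnancies already recognised.

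The observed count enters the primary outcome in section 7 directly, as "expected pregnancies – observed pregnancies] / expected pregnancies", and also gives the secondary pregnancy rate. Section 7 lists "Change in length (shortening / lengthening) of current cycle (days") as a further secondary outcome, and section 9.1 compares menstrual changes between the arms. Section 9.2 assumes that "the fraction of prevented pregnancies in the placebo group is around 52" per cent, with 10 points more on piroxicam as the smallest worthwhile gain.

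Appendix 1, the data collection sheet, is not in the text available for this review.

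**The concern.** The primary outcome is measured by a test that only some women receive, and the bleeding report decides who receives it. A woman who is pregnant but bleeds in a way that is taken for a period leaves follow-up untested. She is not missing under section 9.1, because her outcome has been recorded as no pregnancy. The error therefore leaves no trace in the data, and no planned analysis would reveal it.

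Two features make this worth attention here. The count of pregnancies is small, so single cases matter. And the trial itself treats bleeding and cycle length as things the treatment might alter, so the probability of being tested is not guaranteed to be the same in both arms.

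**Working it through.** **Inputs**
- Prevented fraction (PF) 52% on placebo and 62% on piroxicam, 80% power, type I error 0.05, 10% default, 860 in total: section 9.2.
- LNG failure rate 35/1625 = 2.15%, pooled from two trials: section 2.
- LNG prevented fraction 51.9%: section 9.2.
- Share of true pregnancies missed, m: not in the documents. Assumed at 5%, 10% and 20%.

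**The plan's own figure.** Two proportions, two-sided test, pooled variance, no continuity correction:

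n = [1.960 × √(2 × 0.57 × 0.43) + 0.842 × √(0.52 × 0.48 + 0.62 × 0.38)]² / 0.10² = 384 per group.

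This matches section 9.2. Allowing for default, 384/0.9 gives 427 per arm, or 854, consistent with 860. With 860 recruited, 430 × 0.9 = 387 women per arm are evaluable.

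**Equal misses in both arms.** Only (1 − m) of the pregnancies are seen, so reported PF = 1 − (1 − true PF) × (1 − m).

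| m (assumed) | Placebo | Piroxicam | Difference |
|---|---|---|---|
| 0 | 52.0% | 62.0% | 10.0 points |
| 5% | 54.4% | 63.9% | 9.5 points |
| 10% | 56.8% | 65.8% | 9.0 points |
| 20% | 61.6% | 69.6% | 8.0 points |

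For example, at 10%: 1 − 0.48 × 0.9 = 56.8% and 1 − 0.38 × 0.9 = 65.8%. The ratio of observed pregnancies between the arms is unchanged (0.38/0.48 = 0.79 at every m).

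**Misses in one arm only.** Suppose there is no true effect (52% in both arms) and only piroxicam pregnancies are missed. The false difference is 0.48 × m: 2.4, 4.8 and 9.6 points at 5%, 10% and 20%. To reach 10 points, m = 0.10/0.48 = 21%. Conversely, the same 21% missed on placebo alone would erase a true 52%/62% difference.

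**Counts.** Assume the 2.15% and the 51.9% can be combined, although they may come from different datasets.
- Expected rate: (35/1625)/(1 − 0.519) = 4.48%.
- Model-expected pregnancies per arm: 387 × 4.48% = 17.3.
- Observed: 17.3 × 0.48 = 8.3 on placebo and 17.3 × 0.38 = 6.6 on piroxicam, about 15 in the whole trial.
- One missed pregnancy moves an arm's PF by 1/17.3 = 5.8 points.
- If the expected rate were 3%, 1/(387 × 0.03) = 8.6 points. If it were 8%, 1/(387 × 0.08) = 3.2 points.

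At m = 10%, the expected number missed is 0.8 on placebo and 0.7 on piroxicam. The 21% needed to mimic the target is 0.21 × 8.3, or about 1.7 pregnancies.

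**The case against.** The strongest reply is that the trial asks about a difference between arms, and equal misses shrink that difference. For a superiority claim this is conservative. A reader might infer from the inflated prevented fractions that the trial is set up to show a false benefit. The documents do not support that. A false benefit would require pregnant women on piroxicam to have bleeds accepted as menses more often than pregnant women on placebo, and nothing in the plan says so. Comparing cycle length and menstrual changes across all participants says nothing about bleeding in those who are pregnant. Subjects, clinicians and research staff are blinded (sections 4 and 6.2). If piroxicam delayed menses beyond the visit or made bleeding abnormal, section 6.3 would lead to more testing, not less.

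A reader might also infer that each woman alone decides whether her bleed was normal. Section 6.3 does not say who decides. Spotting and clearly abnormal bleeding should already lead to a test, given the diary, the details collected at the visit and the baseline menstrual history. The gap is confined to bleeding that passes as an ordinary period. Appendix 1 could contain a definition or a test item.

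All of this limits the size and direction of the problem, but the gap remains. Blinding guards against biased judgement. It does not prevent a drug effect on bleeding from changing who is tested. Each arm's prevented fraction is a reported result in its own right, and equal misses still inflate it. The available text gives no rule for accepting a bleed as normal.

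**Conclusion.** The point holds as a weakness in how the primary outcome is ascertained. It is not evidence of a biased comparison. As written, a pregnancy accompanied by apparently normal bleeding is counted as prevented, and the error can only raise the prevented fraction of the arm in which it occurs.

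In the equal-miss scenarios each arm is overstated by about 2 to 10 points, and the difference is understated by 0.5 to 2 points. Misses that differ by arm could create or hide an effect. That is a possibility the design leaves open, not something the documents show.

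The conclusion rests on assumed miss rates, on combining two published figures that may not belong together, and on Appendix 1 not already requiring a test. The sensitivity to single cases is more robust: one missed pregnancy is worth about 3 to 9 points in an arm over the range of expected rates considered, against a target of 10. This is a cheap improvement that should be made. The required 384 per group does not change.

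**What to change.** In section 6.3, replace the conditional test with a urine pregnancy test for every woman at the planned follow-up, whatever bleeding she reports. If Appendix 1 already requires this, section 6.3 should say so.

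Where a test cannot be obtained, classify the outcome by a bleeding criterion that the investigators fix in advance, comparing the recorded onset, duration and amount with the woman's baseline menstrual history. The documents offer no basis for a particular limit, so the investigators should set and justify one. In section 9.1, add a sensitivity analysis of the primary outcome limited to women with a test result, recomputing the expected pregnancies for those same women.

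The cost is about 770 test strips (2 × 387 = 774 evaluable women) and at most 860, at a visit already planned and with a kind of test already done on every woman at baseline. The practical burden falls on women reached only remotely: section 9.1 counts those who can be contacted, and they would need a home test or an attended visit.

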## 7. Study outcomes

### Primary outcome measure:

- Fraction of pregnancies prevented (%)  
[(expected pregnancies – observed pregnancies] / expected pregnancies]  
The number of expected pregnancies will be determined by the Trussell's model (Trussell J et al, Contraception 2003; 67:259-265)

### Secondary outcome measures:

- Pregnancy rate (%)
- Change in length (shortening / lengthening) of current cycle (days)
- Adverse effects

The data collection sheet is included in Appendix 1. All the clinical data are part of the usual consultations for EC provision.

## 8. Assessment of safety

The study medication has been in the market for long time. Being a non-steroidal anti-inflammatory drug (NSAID), it is licensed as an analgesic. Adverse effects are few, and the main side effect is gastrointestinal upset and peptic ulceration. The use of piroxicam for a single dose in this study is not anticipated to be at high risk of causing any significant side effects.

Rarely, piroxicam may lead to potentially fatal skin reactions, e.g. Stevens Johnson Syndrome. Anaphylactic reactions may occur in patients without known hypersensitivity to Piroxicam. Patients with asthma and without known aspirin hypersensitivity will be monitored as signs and symptoms of asthma may occur with the use of Piroxicam. If the above adverse events occur, the subject will be attended by the on-site medical staff and referred to the nearest Accident and Emergency Department.

## 9. Statistics

### 9.1 Statistical tests:

- The efficacy-evaluable population will include all women who are enrolled into the study and can be contacted for a follow-up where the outcome data are collected.
- Cases with missing data in a certain parameter will not be analysed for that specific parameter; no data imputation will be instituted.
- The percentage of pregnancies prevented will be compared between groups by  $\chi^2$  test.
- Logistic regression model using Firth's bias reduction method will be applied to compare the pregnancy rates between groups. Confidence intervals for regression coefficients will be computed by penalised profile likelihood. This is a statistical method recommended for rare events (Puhr R, Heinze G, Nold M, Lusa L, Geroldinger A. Firth's logistic regression with rare events: accurate effect estimates and predictions? Stat Med 2017; 36(14): 2302-2317).
- The rate of occurrence of menstrual changes will be compared between groups using  $\chi^2$  test (for nominal categorical variables) and  $\chi^2$  test for trend (for ordinal categorical variables).

- The rate of occurrence of adverse events will be compared between groups by Fisher's exact test as some of the cells may contain an expected frequency of less than 5.
- Continuous variables between the two groups will be compared by Student's t-test.
- Statistical analyses will be performed using SPSS version 28 (IBM Corporation, New York, USA), MedCalc version 20 (MedCalc Software Limited, Ostend, Belgium) and R package "logistf" Version 4.1.2 (<http://www.r-project.org>).
- P-value <0.05 will be considered as statistically significant.

Two subgroup analyses will be performed. The first subgroup analysis will stratify participants into pre-ovulatory versus post-ovulatory at the time of EC based on blood results of serum oestradiol, progesterone and luteinising hormone level on the day of EC (Li et al, 2016). The second subgroup analysis will stratify participants within versus over the body weight limits recommended for the usual dose of LNG-EC (by the cut-off of body mass index at 26 kg/m^2 and that of body weight at 70 kg).

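### Does the primary outcome need an explicit index-act rule and a planned analysis of later unprotected acts?

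*Combined protocol and SAP*

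**What the plan says.** Section 7 gives the primary outcome as expected minus observed pregnancies, over expected, and adds: "The number of expected pregnancies will be determined by the Trussell's model". It names neither the act covered nor how a pregnancy is traced to an act.

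The observed count comes from section 6.3. A pregnancy test is done at the visit if normal bleeding has not occurred, and "a positive result denotes treatment failure and the woman will be counselled accordingly". Section 9.1 then takes as the efficacy population "all women who are enrolled into the study and can be contacted for a follow-up" where outcome data are collected.

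Later acts are discouraged but recorded. Section 5.1 requires one unprotected act in the current cycle and willingness to abstain from more; section 5.2 excludes women with more than one. Under section 6.2 women are "advised not to have further acts of coitus before menstruation returns", and the diary records "further acts of intercourse, if any, and the contraceptive method used". The follow-up visit collects "any further acts of intercourse and the type of contraception used". None of the tests, the Firth regression or the two subgroup analyses in section 9.1 uses this information.

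**The concern.** The numerator and denominator of the prevented fraction may cover different exposures. If expected pregnancies refer to the index act while any positive test counts as observed, a conception from a later act counts as a failure of emergency contraception although no exposure was added for it. Each arm's prevented fraction would then be too low. That matters because section 9.2 plans on a control value of 52% borrowed from an earlier study, so readers may compare the trial's absolute fractions with outside figures.

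The plan also collects the later acts, which shows it foresees them, yet schedules no report of their frequency or consequences. The obvious suggestion is a sentence in section 7, a table by arm, and a sensitivity analysis leaving out women with a later unprotected act.

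**Working it through.** **The plan's own figure.** With 52% against 62%, two-sided 5% and 80% power (section 9.2), and no continuity correction:

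n = [1.960·√(2·0.57·0.43) + 0.842·√(0.52·0.48 + 0.62·0.38)]² / 0.10² = 383.6, so 384 per group.

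Allowing for 10% loss, 384/0.9 = 427 per group, or 854; the plan recruits 860. Later acts do not enter this calculation.

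**Which act the expected count covers.** Sections 5.1 and 5.2 leave each woman with one unprotected act at entry. Section 6.1 estimates cycle day relative to ovulation at presentation only, and the plan describes no such estimate for later acts. A count including later acts is nowhere described, so the index act is the only workable reading.

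**Which pregnancies are observed.** Section 6.3 with section 9.1 gives an all-pregnancies rule: a positive test at the visit in a followed-up woman is a failure, whichever act caused it. Testing applies only where normal bleeding has not occurred by a visit set as follows: "A follow-up appointment will be arranged about 1-2 weeks after the next expected menstruation". The rule therefore does not attribute pregnancies to acts, but it does define them.

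**Size of the effect.** The documents give no expected pregnancy rate, so two are assumed:

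- 4.48%, from 2.15% (the pooled levonorgestrel failure rate in section 2) divided by 1 − 0.52. This mixes a pooled rate with one study's fraction.
- 8%, purely for range.

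| Per arm of 384 | 4.48% | 8% |
|---|---|---|
| Expected E | 17.2 | 30.7 |
| Observed at 52% / 62% prevented | 8.26 / 6.54 | 14.75 / 11.67 |
| Loss per later-act pregnancy, 100/E | 5.8 points | 3.3 points |
| Prevented, one such pregnancy in each arm | 46.2% / 56.2% | 48.7% / 58.7% |
| Difference | 10.0 | 10.0 |
| Pregnancy-rate ratio, before → after | 0.79 → 0.81 | 0.79 → 0.80 |
| Approximate 95% CI of the ratio, no later acts | 0.29 to 2.19 | 0.37 to 1.68 |

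The interval uses SE(log ratio) = √(1/o₀ + 1/o₁ − 2/384), where o₀ and o₁ are the observed pregnancies.

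As a share of E: if later acts add pregnancies equal to 5%, 10% or 20% of the index-act expected count in both arms, 52/62 becomes 47/57, 42/52 or 32/42. The ratio becomes 0.81, 0.83 or 0.85.

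The constant difference follows from assuming equal additions. One extra pregnancy in the piroxicam arm alone would give 56.2 − 52.0 = 4.2 points at 4.48%, or 58.7 − 52.0 = 6.7 points at 8%. The ratio would be 7.54/8.26 = 0.91 or 12.67/14.75 = 0.86, well inside the intervals above.

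**What excluding women would do.** Take the 4.48% case with an exclusion window left open until menses. Women who conceive have longer to record a later act, so suppose 5% of all women but 10% of index-act failures are dropped. Then E = 16.34, observed = 7.43 / 5.88, prevented = 54.5% / 64.0%, difference 9.5. A window ending at the expected date of menses, dropping 5% of both, returns 52.0 / 62.0. That date can be derived because section 6.1 states "A menstrual history will be taken", but it misplaces acts when the cycle shortens or lengthens, which section 7 lists as an outcome.

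**The case for a change.** The strongest case for a change is that it is cheap and uses data already collected, and that randomisation does not settle everything. Blinded allocation balances the later acts on average, but not necessarily the chance of conceiving from them. Section 2 says levonorgestrel can postpone the LH surge and that COX-2 inhibitors may delay follicle rupture. If ovulation is shifted differently in the two arms, equal later acts could yield unequal pregnancies. With so few expected pregnancies, one or two would be visible in the prevented fraction.

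This much stands: the documents do not establish that later-act conceptions are equal between arms, so one cannot claim that the difference is certainly unaffected. It does not make the planned analysis wrong. A conception after ovulation was postponed by the assigned drug is a consequence of that assignment, and a comparison of all followed-up women properly includes it. Removing women by a self-reported act after randomisation gives up some of the protection of randomisation and could itself introduce bias.

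Recording later acts without a planned analysis is weak evidence of an omission, since section 7 describes the clinical data as belonging to routine consultations.

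**Conclusion.** No change to the plan is needed. Section 7 does leave the index act unnamed, but the single-act entry criteria supply it and any analyst applying the plan would read it that way. The observed count is settled by sections 6.3 and 9.1 together. The aim and hypothesis in section 3 are comparative, and the planned analysis addresses them.

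What remains is a possible understatement of each arm's absolute fraction, by 5.8 or 3.3 points per later-act pregnancy under the two assumed expected rates. The number of such pregnancies is unknown, and is zero if the advice to abstain is followed. The between-arm difference is unchanged if these pregnancies fall equally, which balance of the acts makes plausible but does not guarantee. No planned test, estimate or sample size is shown to be wrong.

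Naming the index act and counting later acts by arm are details that analysts can supply in the report from data already held. An analysis excluding women with later acts is a matter of preference, and a reasonable statistician could decline it.
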